8.2.3 Common Variable Derivations

Variable	Definition/Calculation
Analysis Study Day (Prior to Dose)	Date of Measurement minus First Dose Date in each study part
Analysis Study Day (Post Dose)	Date of Measurement minus First Dose Date +1 in each study part
Scheduled time	Planned time of the assessment. Time in hours of the assessment relative to the planned time of the first drug administration in each study part
Actual Time	Actual time in hours calculated as the sampling data/time minus the date/time of the first drug administration in each study part
Change from Baseline	Post-dose observation minus baseline observation

8.2.4 ADaM Datasets and Metadata

The analysis datasets will be generated in accordance with Clinical Data Interchange Standard Consortium (CDISC) Analysis Data Model (ADaM) Version 2.1.

ADaM compliant datasets will be delivered to the Sponsor. A define.xml file version 2 with the corresponding metadata will be included. Analysis results metadata will be excluded.

At least the following datasets will be generated:

- Subject-level Analysis Dataset (ADSL)
- AEs Analysis Dataset (ADAE)

EDSREP 009 T 01 G Page 15 of 53

Version Date: 26-Aug-2022

- Exposure Analysis Dataset (ADEX)
- Concomitant Medications Analysis Dataset (ADCM)
- Medical History Analysis Dataset (ADMH)
- Laboratory Analysis Dataset (ADLB)
- Vital Signs Analysis Dataset (ADVS)
- ECG Analysis Dataset (ADEG)
- PK Concentrations Analysis Dataset (ADPC)
- PK Parameters Analysis Dataset (ADPP)
- Pharmacodynamic Analysis Dataset (ADPD)

8.3 Software

The statistical analysis and reporting will be done using SAS[®] for Windows[™] Version 9.4 or higher (SAS Institute, Inc.).

PK parameter calculations will primarily be done using Phoenix[®] WinNonlin[®] (WNL) version 8.1 or higher (Certara, Inc.). Additional PK computations may be performed in SAS[®].

8.4 Statistical Methods

8.4.1 Statistical Outlier Determination

No statistical outlier analysis is planned.

8.4.2 Predetermined Covariates and Prognostic Factors

There are no predetermined covariates or prognostic factors.

8.4.3 Hypothesis Testing

No formal hypothesis testing will be done.

8.5 TFL Layout

Report layout will be according to the PRA EDS – International Council for Harmonisation (ICH) E3 compliant – CSR Template. The layout of TFLs will be according to the PRA EDS standards.

Format:

- Page size: A4
- Data in listings will be sorted by study part, subject number, (for Part C) and time point.
- Data in tables will be sorted by study part, immediately part (for Part C) and time point.
- Column titles will be in title case letters.
- All tables and listings will be in landscape format.

Study part refers to ______ 'Part C Main', and 'Part C Extension' if applicable: "Treatment" refers to placebo and various dose levels of study drug in the TFL.

Table, listing and figure shells will be provided together with the SAP.

EDSREP 009 T 01 G Page 16 of 53

Version Date: 26-Aug-2022

9.0 Analysis Sets

Analyses	Safety Set	Pharmacokinetic Set	Pharmacodyna mic Set	Enrolled Set (Part C only)
Disposition Summaries	√	✓	✓	✓
Demographics	✓	✓	✓	✓
Baseline Characteristics	√			
Medical History	✓			
Treatment Exposure	✓			
AE Summaries	√			✓
CM Summaries	✓			
Other Safety Assessments	✓			
PK Concentrations Summaries		✓		
PK Parameters Summaries		✓		
PD Parameters Summaries			√	

9.1 Safety Set

All subjects who have received at least 1 dose of AZP-3601 or placebo.

9.2 Pharmacokinetic Set

All subjects who have received at least 1 dose of AZP-3601 and provided sufficient bioanalytical assessment results to calculate reliable estimates of the PK parameters.

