15.2 Pharmacokinetic Summaries

15.2.1 Pharmacokinetic Concentrations

All AZP-3601 plasma concentrations will be reported under PK population set with data handling of PK Data Set and PK Data Set Info (for information only). Under PK Data Set, analyses on the concentrations will be performed with values under LLOQ set as "BQL". Under PK Data Set Info, AZP-3601 plasma concentration will include the concentrations extrapolated from the analyte response under the LLOQ (for information purpose); values under LLOQ will either be a "No peak" or an actual value between 0 and the LLOQ value (i.e. 50 pg/mL). The Inclusion of the informative PK concentrations ("No peak" and actual value between 0 and the LLOQ) in the analyses under PK Data Set Info will be performed for information only. The conventions to be applied for "No peak" under PK Data Set Info will be the same as the one use for BQL under PK Data Set. Descriptive statistics and PK concentration plots will be conducted on both data sets.

Descriptive statistics (n, 0<n<LLOQ, n with imputed 0, arithmetic mean, SD, geometric mean, geometric CV(%), median, min, and max) will be used to summarize the plasma concentrations for AZP-3601 by scheduled time point by study part and treatment (for Parts A and B)/cohort (for Part C). Plasma concentrations for AZP-3601 below the quantifiable limit (BQL) will be set to zero in the computation of descriptive statistics. Geometric means and geometric CV(%) will be presented as 'NC' (not calculable) if there is at least one BQL value imputed by zero.

Linear and semi-logarithmic plots of the arithmetic mean plasma concentration with SD by scheduled
sampling time will be provided by study part and
plots will show time in hours. In Part
C, the MAD treatments will be presented in one plot per day. In addition, overlay plots for the MAD
treatments will be presented,
showing Day 1, Day 14 and Day 28 in one plot for Part C (one plot per cohort). If more than half of the subjects for a given timepoint have BQL values, then no mean profiles will be provided.
Combined individual concentration-time profiles will be presented graphically on both a linear and a semi-logarithmic scale for each

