15.2.2 Pharmacokinetic Parameters

PK parameters for AZP-3601 will be estimated using non-compartmental methods with WNL under PK population set with data handling of PK Data Set and PK Data Set Info (if meaningful by the data obtained). Parameters will first be derived with values under LLOQ set as "BQL" (i.e. using PK Data Set). The inclusion of the informative PK concentrations ("No peak" and actual value between 0 and the LLOQ) in the calculation of the parameters will be performed for information only (i.e. using PK Data Set Info). Descriptive statistics will be conducted on both data sets if meaningful by the data obtained.

The plasma PK parameters will be estimated from the concentration-time profiles. In estimating the PK parameters, BQL values at the beginning of the profile will be set to zero. BQL values that occur after the first quantifiable point will be considered missing. Values that are embedded between BQLs, or quantifiable values occurring after two or more BQLs, will be set to missing at the discretion of the pharmacokineticist. Actual sampling times, rather than scheduled sampling times, will be used in all computations involving sampling times. If the actual time or dose time is missing, the scheduled time may be substituted in order to calculate the PK parameter.

EDSREP 009 T 01 G Page 24 of 53

Version Date: 26-Aug-2022

The points to be included in the k_{el} range will be determined by the pharmacokineticist after inspection of the semi-log concentration-time profiles. At least 3 points will be required to be used. The C_{max} data point will not be included.

Parameters based on %AUC $_{extra}$ >20% or Adj R 2 \leq 0.80 will be flagged but not excluded from statistical analysis.

Descriptive statistics (n, arithmetic mean, SD, geometric mean, geometric CV(%), median, min, and max) will be used to summarize the calculated PK parameters by study part and treatment (for Parts A and B) /cohort (for Part C). For t_{max}, only n, median, min and max will be presented.

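### PK concentration summaries are confined to a set defined by parameter evaluability, which can drop patients with mostly unquantifiable values and may bias mean concentrations upward

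*SAP*

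**What the plan says.** **Which set is used.** In the SAP 9.0 table, the row "PK Concentrations Summaries" is ticked for the Pharmacokinetic Set alone. SAP 15.2.1 agrees: "All AZP-3601 plasma concentrations will be reported under PK population set". That holds for both data-handling versions: PK Data Set, where anything under the LLOQ of 50 pg/mL is BQL, and PK Data Set Info, which uses extrapolated values below that limit for information.

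**Who is in the set.** SAP 9.2 requires at least one dose of AZP-3601 and that the subject "provided sufficient bioanalytical assessment results to calculate reliable estimates of the PK parameters". It does not define sufficient or reliable, and does not say which parameters or which days must be estimable.

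**How BQL values are treated.** SAP 15.2.1: "Plasma concentrations for AZP-3601 below the quantifiable limit (BQL) will be set to zero in the computation of descriptive statistics". Each summary also counts the values imputed as zero. The geometric mean and geometric CV become NC once any BQL value at that time point has been imputed as zero. For plots: "If more than half of the subjects for a given timepoint have BQL values, then no mean profiles will be provided".

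**How weak parameter estimates are treated.** Under SAP 15.2.2, parameters with more than 20% extrapolation or an adjusted R² of 0.80 or less "will be flagged but not excluded from statistical analysis".

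**What is shown for everyone.** SAP 9.4 bases all listings on all subjects and has the disposition table report the membership of each set.

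**The concern.** The entry test does not fit the analysis. Whether a terminal slope or an AUC can be estimated reliably has no bearing on whether a measured concentration at 10 minutes can be averaged. Because reliable estimation depends on having quantifiable values, the test can select on the outcome being summarised: patients with the lowest concentrations are the ones most at risk of leaving the summary.

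BQL-related exclusion is plausible here. The SAP plans a separate data set for values below 50 pg/mL, and SAP 7.1 expects fast elimination. The protocol takes six post-dose PK samples per profile, the last at 2 hours (notes to Tables 3 and 4).

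PK in patients is a secondary objective, and each cohort has about 12 patients, so one or two exclusions can move a mean visibly. Without an operational rule, membership could also be settled after the concentrations have been seen.

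**Working it through.** The plan states no exposure or sample-size figure on this point, so there is nothing of its own to reproduce.

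**Inputs.** N = 12 per cohort (SAP 6.0, approximate). BQL = 0 in descriptive statistics and LLOQ 50 pg/mL (SAP 15.2.1). The number k of patients dropped is not in the documents; 0 to 4 is an assumed range.

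**1. Dropped patients who are all BQL.** Let S be the sum of concentrations at a time point. Under the BQL = 0 rule, with everyone included, the mean is S/N. Dropping k patients who each contribute zero gives S/(N − k). The ratio is N/(N − k).

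| k dropped | 12/(12 − k) | Inflation of the mean |
|---|---|---|
| 0 | 1.000 | 0% |
| 1 | 1.091 | 9.1% |
| 2 | 1.200 | 20.0% |
| 3 | 1.333 | 33.3% |
| 4 | 1.500 | 50.0% |

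**2. Dropped patients with some quantifiable values.** Let their mean at that time point be r times the mean of those retained. The ratio becomes N/[(N − k) + k·r]. With k = 2 and r = 0.5 this is 12/(10 + 1) = 12/11 = 1.091, or 9.1% instead of 20.0%. Since r cannot be negative, the table gives upper bounds for each k.

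**3. Display rules.** With 7 of 12 BQL (58.3%), 15.2.1 withholds the mean profile. If two all-BQL patients are dropped, 5 of 10 (50.0%) is no longer more than half, and the profile is shown. In the same way, if the only BQL values at a time point belong to dropped patients, a geometric mean that should read NC is printed as a number.

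**4. How far the answer depends on unknown concentrations.** A simulation of 400,000 patients used the protocol sampling times and assumed lognormal peaks with CV 40% or 80%, an absorption half-life of 5 minutes and an elimination half-life of 20 minutes. Each patient had one profile and was excluded if fewer than 1, 3 or 4 points reached 50 pg/mL. None of these kinetic values or cut-offs comes from the documents.

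| Assumed geometric mean peak (pg/mL) | Patients excluded | Inflation of the mean at peak |
|---|---|---|
| 60 | 32% to 62% | 47% to 95% |
| 100 | 4% to 29% | 4% to 32% |
| 200 | 0% to 6% | 0% to 6% |
| 400 | at most 0.6% | at most 0.5% |

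Exclusion of 15% at random, unrelated to concentration, gave no bias. The upward direction therefore comes from exclusion because of low values.

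**The case against.** The strongest reply is that the text shows only that patients could be lost.

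- **Kel is not the entry test.** A reader might infer from the three-point rule for kel that a patient without a terminal slope is out. Section 9.2 does not name kel, and Cmax, tmax and AUC to the last quantifiable point need no terminal fit. Sufficient results could also mean enough valid samples, and a BQL result is a valid assay result. This stands; the remaining fault is that 9.2 does not say which reading applies.
- **Membership is per subject.** Part C has serial profiles on Days 1, 14 and 28, and on Day 84 in the extension, so one evaluable profile may keep a patient in. This stands and lowers the likely number of exclusions.
- **The BQL rule has other uses.** Setting BQL to zero is also needed for predose and late samples of patients inside the set, so it does not prove that wholly BQL patients were meant to be counted. This stands. Still, if the set removes such patients first, the zero rule never reaches them.
- **Flag-and-retain is not a contradiction.** A reader might infer that 9.2 conflicts with 15.2.2. The latter is a parameter-level rule for members of the set, and if anything suggests that a poor terminal fit alone should not exclude anyone.
- **The listings show everyone.** Exclusions would be visible and means could be recalculated. True, but the summary tables and figures would remain uncorrected.

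**Conclusion.** The point holds as a conditional one. The SAP ties concentration summaries to a parameter-evaluability set without an operational rule. That set can omit patients whose values are all or mostly BQL, and the PK Data Set Info analysis does not restore them. If that happens, mean concentrations may be biased upward relative to the SAP's own zero rule, and profiles or geometric means that should be withheld may appear. The bounds for a cohort of 12 are those in the first table. They assume that every dropped patient is BQL at the time point in question.

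Two stronger readings are not supported. One is that the rule does remove low-exposure patients and does inflate the means: the documents give neither expected concentrations nor BQL counts, so the effect may be nil. The other is that comparisons across doses are distorted: Part C is summarised by cohort with dose increases allowed within cohort, and no text is visible under the dose-proportionality heading (15.2.2.1), so no effect there can be assessed.

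The consequence is confined to descriptive secondary PK summaries. The Pharmacokinetic Set is not used for the safety analyses, and SAP 8.4.3 plans no formal hypothesis testing.

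**What to change.** Add a concentration set to SAP 9.0 and 9.2 and refer to it in 15.2.1 for both data-handling versions: all patients with at least one dose of AZP-3601 and at least one post-dose concentration result, BQL results included. State any other reasons for exclusion in advance.

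For the parameter summaries only, judge evaluability parameter by parameter, show n for each, and keep the flag-but-retain rule of 15.2.2.

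The cost is SAP wording and one more population flag; no new data are needed. The downside is more NC geometric means and possibly more withheld mean profiles, both of which 15.2.1 already provides for. If no patient would have been excluded for BQL values or missing results, the concentration summaries do not change.

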9.3 Pharmacodynamic Set

All subjects belonging to the safety set and for whom the PD data are considered to be sufficient and interpretable.

9.4 Enrolled Set (Part C only)

All patients who sign the informed consent form.

The table of "Disposition Summaries" will be presented from "All Subjects", including summarizing the members of each analysis set. Moreover, all the listings will also be presented from "All Subjects".

10.0 Subject Disposition

All disposition data will be listed.

EDSREP 009 T 01 G Page 17 of 53

Version Date: 26-Aug-2022

members of each analysis set will be presented. The number and percentage of subjects who withdrew from the study prematurely and a breakdown of the corresponding reasons for withdrawal will also be presented. Summaries will be reported by study part and treatment, as well as overall within each part.

11.0 Protocol Deviations and Violations

Protocol deviations will be collected and entered into the Clinical Trial Management System (CTMS) per clinical monitoring Standard Operating Procedures. From CTMS, protocol deviations will be pulled into study data tabulation model (SDTM). Important protocol deviation data will be listed by subject.

12.0 Demographic and Baseline Characteristics

12.1 Demographics

All demographic data will be listed by subject.

Subject demographics will be summarized descriptively for all subjects by study part and ______/cohort (for Part C) as well as overall within each part. The summary will include the subjects' age (in years), gender, race (if available), ethnicity, weight (in kg), height (in cm), and body mass index (BMI) (in kg/m²) at baseline. In addition, for Part C, the number and percentage of subjects will be summarized by age group '<45 years', '≥ 45 and <65 years' and '≥65 years'. Demographics will be summarized for the safety, PK, PD and enrolled sets if applicable.

12.2 Medical History and Disease under Study

Medical history will be listed by subject. Medical history data will be coded according to the Medical Dictionary for Regulatory Activities (MedDRA) version 23.1.

Medical history will be summarized by system organ class (SOC) and preferred term (PT). The number and percentage of subjects will be presented by study part and _______/cohort (for Part C).

For Part C, all the information related to disease under study will be listed by patient. A summary table will be provided for the duration (in years) and the etiology of hypoparathyroidism. Furthermore, menopause status will be summarized using the frequency of patients with or without menopause based on the total number of female patients, and using the time since menopause (years).

12.3 Other Baseline Characteristics

For Part C, a summary table and a listing will be provided for the following baseline values:

- Prescribed active vitamin D
- Prescribed active vitamin D in category (low, medium, high):
 - $_{\odot}$ Calcitriol: low dose 0-0.25 µg/day, medium dose >0.25-0.5 µg/day, high dose >0.5 µg/day.
 - \circ Alfacalcidiol: low dose 0-0.50 μg/day, medium dose >0.50-1.0 μg/day, high dose >1.0 μg/day
- Prescribed calcium
- Prescribed calcium in category:
 - o 0-2000 mg/day
 - o >2000 mg/day
- Serum total calcium
- Serum phosphate

EDSREP 009 T 01 G Page 18 of 53

Protocol: AZP-3601-CLI-001 Version Date: 26-Aug-2022

- Albumin-adjusted serum calcium
- Serum 25-Hydroxyvitamin D
- Serum 1,25-Dihydroxyvitamin D
- 24-Hour urinary calcium (mg/24h)
- 24-Hour urinary calcium adjusted by creatinine
- FECa of calcium
- FECa of calcium in category
 - o 0-2%
 - o > 2%
- Bone turnover biomarkers
- e-GFR

The other baseline characteristics will be listed, including results of pregnancy tests, serology tests, drug and alcohol screen, SARS-CoV-2 Polymerase Chain Reaction (PCR) test and childbearing potential (Part C only).

13.0 Concomitant Medications

Prior and concomitant medications (drug treatment), categorized by standardized medication group according to the World Health Organization (WHO) Drug Dictionary (WHODrug Global B3 SEP2020), will be listed by subject. Medications with an end date prior to the first dose of study drug within each study part will be considered prior medications and will be identified in the listing. Any medication taken after the first dose of study drug, including those who started prior to the first dose of study and continued past that date will be considered concomitant medications. If a partial date allows a medication to be considered concomitant it will be categorized as such.

Concomitant medications (drug treatment) will be summarized by standardized medication group and /cohort (for Part C) in each study part. The number and percentage of subjects using at least one medication within each standardized medication group will be presented by /cohort (for Part C) in each study part.

In addition, prior and concomitant medications (non-drug treatment) will also be listed.

14.0 Treatment Compliance and Exposure

Exposure data of study drug, collected by CRF, will be listed by subject. In Part C, exposure data of study drug, collected by diary, will also be listed by subject. If applicable, date and time of meal intake and comments will be listed.

For Part C, exposure data of study drug will be summarized by cohort for

- Dose exposure parameters separately by main treatment period and extension phase include:
 - o Total actual dose received (µg) (Sum of all doses administered)
 - Number of doses received
 - Duration of exposure (in days) = last dose date first dose date + 1
 - Dose Intensity (μg/day) = total actual dose received / duration of exposure
 - o Relative Dose Intensity (ratio) = total actual dose received / total planned dose
- Dose increases during the main treatment period include:
 - o Doses increases at Day 15 = Yes / No (doses at Day 15 versus doses at Day 1)

EDSREP 009 T 01 G Page 19 of 53

Version Date: 26-Aug-2022

- Doses increases after Day 15 = Yes / No (doses at Day 16 or later up to Day 28 versus doses at Day 1)
- Doses increases or decreases during the extension phase (versus actual dose at Day 28) include:
 - Number of patients with one increase only (without decrease)
 - o Number of patients with at least two increases (without decrease)
 - Number of patients with one decrease only (without increase)
 - Number of patients with at least two decreases (without increase)
 - o Number of patients with both increase and decrease
 - o Number of patients with no change in dose

Study drug dispensing and returning will be listed by subject.

15.0 Pharmacokinetic Analyses

15.1 Pharmacokinetic Variables

15.1.1 Plasma Variables

15.1.1.1 Plasma PK Concentrations

Plasma AZP-3601 concentrations

15.1.1.2 Plasma PK Parameters

PK Parameters for AZP-3601 as defined in Table 1

EDSREP 009 T 01 G Page 20 of 53

Statistical Analysis Plan AZP20005-20005X

Protocol: AZP-3601-CLI-001 Version Date: 26-Aug-2022

Table 1 Plasma AZP-3601 PK Parameters

Parameter	AND C Day 1	AND PART C DAY 28 and DAY 84	Description	SAS Programming Notes
C _{max}	×	Х	Maximum plasma concentration. Observed peak analyte concentration obtained directly from the experimental data without interpolation, expressed in concentration units.	Cmax from WNL. C_{max} will be presented as "Cmax" in the TFL.
Ctrough		Х	Trough plasma concentration.	Derived in SAS C_{trough} will be presented as "Ctrough" in the TFL.
C _{min}		Х	Minimum plasma concentration (predose concentration excluded)	Cmin from WNL. C _{min} will be presented as "Cmin" in the TFL.
t _{max}	×	Х	Time to maximum plasma concentration. First observed time to reach peak analyte concentration obtained directly from the experimental data without interpolation, expressed in time units.	Tmax from WNL. t _{max} will be presented as "Tmax" in the TFL.
AUC _{0-t}	×		Area under the plasma concentration-time curve (time 0 to time of last quantifiable concentration).	AUClast from WNL. AUC _{0-t} will be presented as "AUClast" in the TFL.
AUC _{0-inf}	X		Area under the plasma concentration-time curve (time 0 to infinity). Calculated as: $AUC_{0-inf} = AUC_{0-t} + C_{last}/k_{el}$, where C_{last} is the observed concentration at time t, where t is the last point with a concentration above the lower limit of quantification. Percent extrapolation less than or equal to 20% and an adjusted r^2 greater than 0.80 are required to obtain a reliable AUC_{0-inf} .	AUCINF_obs from WNL. AUC _{0-inf} will be presented as "AUCinf" in the TFL. If %AUC _{extra} >20% then parameter is flagged. If Adj $R^2 \le 0.80$ then parameter is

EDSREP 009 T 01 G Page 21 of 53

Version Date: 26-Aug-2022

Parameter	AI C Da		8	SAS Programming Notes
				flagged.
%AUC _{extra}			Percentage of estimated part for the calculation of AUCinf: Calculated as: ([AUC _{0-inf} – AUC _{0-t}]/ AUC _{0-inf})*100%.	AUC_%Extrap_obs from WNL. %AUC _{extra} will be presented as "AUC%extrap" in the TFL, and listed only.
AUC ₀₋₆		Х	Area under the plasma concentration-time curve from time zero up to 6 hours.	AUC0-6 from WNL AUC0-6 will be presented as "AUC(0-6)" in the TFL.
AUC ₀₋₁₂		Х	Area under the plasma concentration-time curve from time zero up to 12 hours.	AUC0-12 from WNL AUC0-12 will be presented as "AUC(0-12)" in the TFL.
AUC ₀₋₂₄		Х	Area under the plasma concentration-time curve from time zero up to 24 hours.	AUC0-24 from WNL AUC0-24 will be presented as "AUC(0-24)" in the TFL.
k _{el}		X	Terminal phase rate constant calculated by linear regression of the terminal log-linear portion of the concentration vs. time curve. Linear regression of at least three points and an adjusted r² greater than 0.80 are required to obtain a reliable kel.	Lambda_z from WNL. k_{el} will be presented as "Kel" in the TFL, and listed only If Adj $R^2 \le 0.80$ then parameter is flagged.
t _{1/2}		X	Terminal phase half-life expressed in time units. adjusted $\rm r^2$ greater than 0.80 is required to obtain a reliable $\rm t_{1/2}$.	HL_Lambda_z from WNL. $t_{1/2}$ will be presented as "t1/2" in the TFL. If Adj $R^2 \le 0.80$ then parameter is flagged.

EDSREP 009 T 01 G Page 22 of 53

Statistical Analysis Plan AZP20005-20005X Protocol: AZP-3601-CLI-001 Version Date: 26-Aug-2022

				VOIDION Bato. 20 7 tag 2022
Parameter	AND C Day 1	AND PART C DAY 28 and DAY 84	Description	SAS Programming Notes
CL/F			Apparent oral clearance, calculated as dose/AUC _{0-inf} .	CL_F_obs from WNL. If %AUC _{extra} >20% or Adj R ² ≤ 0.80 then parameter is flagged.
CL _{ss} /F		X	Apparent oral clearance at steady state, calculated as dose/AUC _{0-tau} where tau =6h (Parts B and C).	CLss_F from WNL CLss/F will be presented as "CLss/F" in the TFL.
Vz/F		Х	Apparent volume of distribution at terminal phase, calculated as (CL/F)/kel (Part A), or as (CLss/F)/kel (Parts B and C).	VZ_F_obs from WNL. If %AUC _{extra} >20% or Adj R ² ≤ 0.80 then parameter is flagged.
Rac		Х	Accumulation ratio, based on AUC _{0-tau} of Day 14 (Part B) or Day 28 (Part C) vs Day 1 where tau = 6h (Parts B and C).	Calculated in SAS. Rac will be presented as "Rac" in the TFL.
Adj R²	X		Goodness of fit statistic for the log-linear terminal elimination phase of the concentration-time profile identified by least-squares linear regression and adjusted for the number of points (minimum of 3) used in the estimation of k_{el} .	"Rsq_adjusted" from WNL. Adj R ² will be presented as "Adj R2" in the TFL and listed only.

Note: AUCs will be calculated using linear up / log down, expressed in units of concentration x time.

EDSREP 009 T 01 G Page 23 of 53

Version Date: 26-Aug-2022

